1. OBJECTIVES

1.1 Primary Objectives

- Estimate the objective response rate (ORR) using RECIST 1.1

1.2 Secondary Objectives

- Estimate the 6-month and median progression free survival (PFS) rates
- Estimate the 2-year and median overall survival (OS) rates
- Evaluate the safety of trametinib in patients with epithelioid hemangioendothelioma
- Evaluate patient-reported symptoms using NIH PROMIS global health; pain intensity, interference and behavior short form inventories prior to, after 4 weeks and after 6 months (if stable or better disease) of treatment, and on evidence of disease progression

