5.5 Duration of Therapy

In the absence of treatment delays due to adverse event(s), treatment may continue for 52 cycles or until one of the following criteria applies:

- Disease progression per RECIST,
- Clinical progression,
- Intercurrent illness that prevents further administration of treatment,

- Unacceptable adverse event(s),
- Patient decides to withdraw from the study
- Pregnancy
 - All women of child bearing potential should be instructed to contact the investigator immediately if they suspect they might be pregnant (e.g., missed or late menstrual period) at any time during study participation.
 - The investigator must immediately notify CTEP in the event of a confirmed pregnancy in a patient participating in the study.
- General or specific changes in the patient's condition render the patient unacceptable for further treatment in the judgment of the investigator.

Patients with clinical progression or disease progression per RECIST who are benefitting from trametinib in reduction of tumor-related symptoms may continue on treatment with trametinib after discussion with the Study PI and CTEP Medical Monitor and approval.

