5.6 Duration of Follow Up

Patients will be followed for 24 months after initiation of trametinib unless the patient remains on active treatment beyond 24 months. In that case, follow-up will be continued until 6 months after discontinuation of treatment or until death, whichever occurs first. If the patient discontinues therapy prior to 24 months, follow-up will continue for 6 months after discontinuation or 24 months after initiation of trametinib, whichever is longer. Patients removed from study for unacceptable adverse event(s) will be followed until resolution or stabilization of the adverse event.

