10. STUDY CALENDAR

Baseline evaluations are to be conducted within 2 weeks prior to patient registration. Tumor imaging, cardiac evaluation and ophthalmology evaluations must be done within 30 days prior to patient registration. In the event that the patient's condition is deteriorating, laboratory evaluations should be repeated within 48 hours prior to initiation of the next cycle of therapy. The window for cycle visits is +/- 7 days.

	Pre-Study	Wk 1	Wk 2	Wk 3	Wk 4	Wk 5	Wk 6	Wk 7	Wk 8	Wk 9	Wk 10	Wk 11	Wk ⁱ 12	Off Treatment
Trametinib Daily		A	A	A	A	A	A	A	A	A	A	A	A	
Informed consent	X													
Archival tumor tissue sent for TAZ-CAMTA1 FISH	X													
Demographics	X													
Medical history	X													
Concurrent meds	X	X-----									X			
Physical exam	X	X		X		X				X				X
Vital signs	X	X				X				X				X
Height	X													
Weight	X	X				X				X				X
Performance status	X	X				X				X				X
CBC w/diff, plts	X	X		X		X				X				X
Serum chemistry ^a	X	X		X		X				X				X
ESR, CRP ^b	X					X								
Plasma collection for CTGF ^b	X					X								
EKG	X													
Echocardiogram or MUGA ^c	X													Every 12 weeks (+/- 14 days) (use same methodology for baseline and follow up).
Ophthalmology exam ^d	X													
Adverse event evaluation		X-----									X			X
Tumor measurement ^e	X													X
Radiologic evaluation ^f	X													X
Pregnancy test ^g	X													
Optional fresh biopsy of tumor	X				X									
NIH PROMIS Questionnaire ^h	X				X									

A: Trametinib: Dose as assigned; to be taken daily

a: Comprehensive metabolic panel. The panel should include albumin, alkaline phosphatase, total bilirubin, bicarbonate, BUN, calcium, chloride, creatinine, glucose, potassium, total protein, SGOT [AST], SGPT [ALT], sodium.

b: Biomarker assessment: ESR-westergren method preferred and CRP, to be performed by local lab prior to therapy, after 4 weeks and 6 months of treatment (for patients with stable for better disease), at time of objective response and at progression. Plasma for

- determination of CTGF level to be obtained at the same time points and sent to central lab for analysis.
- c: The same modality (ECHO or MUGA) should be used at baseline and at follow-up
- d: Ophthalmology exams should be obtained at baseline, and if clinically indicated, during study. Ophthalmology exam should include Ocular Coherence Tomography, fundoscopy, tonometry, visual field examination, and corrected visual acuity assessments.

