- e: Tumor digital files to be sent to QARC for tumor volume assessment.
- f: Tumor measurements do not need to be repeated if patient ends treatment because of documented tumor progression by imaging.
- g: Blood or urine pregnancy test (women of childbearing potential).
- h: NIH PROMIS global health, pain intensity, interference and behavior short form inventories to be obtained prior to trametinib treatment, after 1 month and 6 months of treatment, and on evidence of disease progression or response.
- i: For patients remaining on treatment after week 12, evaluations will include physical exam, weight, performance status, complete blood count with differential and platelet count, and serum chemistry at least once per cycle.

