Secondary objectives of the 6-month PFS rate, median PFS, and 2-year OS rate will be determined from analyses of patients with *TAZ-CAMTA1* translocation positive EHE. Evaluation of the safety of trametinib, and patient reported symptoms using NIH-PROMIS questionnaires will be determined from analyses of all patients who started treatment with trametinib.

Progression-free survival will be calculated from time of first dose of study medication to occurrence of radiologic tumor progression per RECIST1.1, clinical progression based on treating physician's assessment or death from any cause. Overall survival will be calculated from the time of first dose of study drug to occurrence of death from any cause. Patients who are registered and are determined to be eligible for study treatment but do not start study drug will be replaced. All patients who receive study drug for any period of time will be evaluable for toxicity. The rates of adverse events occurring in at least 5% of subjects and rates of grade 3-5 adverse events will be tabulated by system and term using Common Terminology Criteria of Adverse Events (CTCAE). For dose adjustment schedule see Section 6.1. PROMIS questionnaires will be scored according to recommended standardized system and t-scores generated. A mixed model will be used to analyze change in t-scores over time. Whether or not having evidence of disease progression will be used as a time-dependent variable in the mixed model with adjustment of other potential confounding variables.

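### After week 4 every PROMIS form depends on staying on treatment or on a disease event, so the 6-month symptom estimate rests on a selected group.

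*Combined protocol and SAP*

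**What the plan says.** Patient-reported symptoms are a secondary objective. Section 1.2 asks for the PROMIS inventories (global health; pain intensity, interference and behavior) before treatment, "after 4 weeks and after 6 months (if stable or better disease) of treatment, and on evidence of disease progression".

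Footnote h of the calendar in section 10 gives a different schedule after baseline: "after 1 month and 6 months of treatment, and on evidence of disease progression or response". It omits the stable-or-better condition and adds a form at response. The calendar row labelled "NIH PROMIS Questionnaire" is marked at Pre-Study and week 4 only. Its Off Treatment cell is empty, although physical exam, vital signs, weight, performance status, laboratory tests, adverse events and tumor assessment are all marked there.

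Section 5.5 lists toxicity and withdrawal among the reasons for ending treatment. For patients who stop early, section 5.6 says that "follow-up will continue for 6 months after discontinuation or 24 months after initiation of trametinib, whichever is longer".

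On analysis, section 13.1 says that "patient reported symptoms using NIH-PROMIS questionnaires will be determined from analyses of all patients who started treatment with trametinib". The method is: "A mixed model will be used to analyze change in t-scores over time". It adds: "Whether or not having evidence of disease progression will be used as a time-dependent variable in the mixed model". The same sentence allows for other confounders without naming them.

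**The concern.** Only the baseline and week-4 forms are fixed in time for everyone. After that, whether a patient is asked about symptoms depends on how the patient is doing. Patients who stop between week 4 and month 6 because they tolerate the drug poorly, without progression or response, have no form due when they stop and none at 6 months. The analysis is nevertheless described as covering everyone who started treatment.

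If those patients would have scored differently at 6 months, the estimated change describes those who tolerated treatment and remained free of progression, not the treated population. There is no control arm against which a selection effect would show. The two versions of the schedule also leave a site unsure who owes a 6-month form and whether a responder owes an extra one.

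**Working it through.** **Which form each patient owes after week 4**

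| Patient | Section 1.2 | Footnote h |
|---|---|---|
| On treatment at 6 months, stable or better | 6-month form | 6-month form |
| Treated past progression to 6 months (possible with approval, section 5.5) | progression form only | progression form and 6-month form |
| Response | no extra form | extra form at response |
| Progression, on or off treatment | progression form | progression form |
| Stops between week 4 and month 6, no progression or response | none at stop, none at 6 months | none at stop, none at 6 months |

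The last row does not depend on reading the empty calendar cell correctly, because neither text makes stopping treatment a trigger. The missing form could be collected. A patient who stops at month 3 is followed to the later of 3 + 6 = 9 months and 24 months, that is to month 24, so the 6-month point falls within follow-up.

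**How many patients**

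The plan gives no expected PROMIS completion rate, so there is no figure to reproduce. The following is an illustration.

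- Treated patients, N: 27 fusion-positive, plus 3 with no fusion detected and 1 with insufficient tissue in stage I (section 13.1) = 31, taking those four as having started trametinib. More are possible in stage II.
- Progression-free at 6 months, S: low value 38.4%, from the sorafenib study in section 2.1. High value from the bevacizumab median of 39.1 weeks in the same section, about 9 months; if exponential, 0.5^(6/9) = 0.63.
- Share of progression-free patients stopped for toxicity by 6 months, d: not given. The only overall adverse-event withdrawal rate in the text is 23%, in the AML/MDS study (section 2.2.1.2). I take 23% as an assumption, with 5% to 30% as a range.

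Missed for this reason = N × S × d:
- d = 23%: 31 × 0.384 × 0.23 = 2.7, and 31 × 0.63 × 0.23 = 4.5.
- Range: 31 × 0.384 × 0.05 = 0.6, to 31 × 0.63 × 0.30 = 5.9.

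6-month forms under section 1.2 = N × S × (1 − d):
- d = 23%: 31 × 0.384 × 0.77 = 9.2, and 31 × 0.63 × 0.77 = 15.0.
- Range: 31 × 0.384 × 0.70 = 8.3, to 31 × 0.63 × 0.95 = 18.6.

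**Whether the mixed model repairs it**

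A mixed model is unbiased if the observed scores and the covariates explain who is missing. Progression, the one named time-dependent term, does not separate a progression-free toxicity stopper from a progression-free patient still on treatment. The observed scores for such a stopper are baseline and week 4. In the phase 3 melanoma trial (section 2.2.1.3), cardiomyopathy had a median onset of 63 days and only 5 of 14 cases appeared in the first month, so the week-4 form can precede the problem.

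To see the mechanism, suppose stoppers would score 5 to 10 T-score points worse on a pain scale at 6 months (assumed). Leaving them out shifts the progression-free mean by d × difference: 0.23 × 5 = 1.15, and 0.23 × 10 = 2.3 points, in the favourable direction. A simulated random-intercept model (between-patient SD 7, residual SD 5, both assumed) left a bias of 1.0 to 1.1 points for a 5-point difference and 1.8 to 2.3 for a 10-point difference. The smaller value in each pair applies when half the difference already shows at week 4. Under these assumptions the model removes little of the shift.

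**The case against.** Several stronger readings are tempting, and the documents do not support them.

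- *Toxicity stoppers give nothing after week 4.* The progression form is not restricted to patients on treatment, follow-up continues, and the median PFS values quoted for EHE are 4.8 months, 6 months and 39.1 weeks. Many stoppers would be expected to progress in follow-up and trigger a form. An earlier responder may also have given one under footnote h. This stands. It does not supply a 6-month value, because the progression form is itself triggered by outcome.
- *Most patients are lost.* Applying 38.4% to the 27 patients in the design leaves 27 × 0.616 = 16.6 without a 6-month form. Those are patients who progressed or died, and progression does trigger a form. The PROMIS population is also all treated patients, not 27.
- *The 6-month result will look too good.* The forms cover pain and global health, while the commonest toxicities are rash and diarrhea. Nothing in the documents shows that stoppers would score worse. Progression forms sample bad moments and can pull the overall curve the other way.
- *Stoppers leave the analysis.* The mixed model keeps their baseline and week-4 scores, and section 13.1 leaves room for further confounders. Some toxicity starts early: median onset of skin toxicity was 15 days in the phase 3 trial, so week 4 may capture part of it.

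It is also fair that this is a descriptive secondary objective with no decision rule, and that tolerability is assessed separately through adverse events in all treated patients. This limits the weight of the point but does not close the gap in the schedule.

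**Conclusion.** The point holds in a limited form. After baseline and week 4, PROMIS collection depends on outcome, and a patient who stops between week 4 and month 6 without progression or response gives no form at that point and no 6-month form. The model in section 13.1 names progression but not discontinuation, so its 6-month estimate rests on a selected group and may be biased. A favourable direction is plausible but not shown, and the size cannot be derived from the documents.

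On the assumptions above, about 3 to 4 of 31 patients would be missed for this reason at a 23% stopping share, and between 0.6 and 5.9 over the wider range. The count rests on a rate borrowed from another disease and on progression-free rates from other drugs. Baseline and week-4 data are not affected, and neither is the primary response analysis.

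Separately, and without any assumption, section 1.2 and footnote h disagree on the stable-or-better condition and on the response-triggered form. The change is worth making because it is cheap.

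**What to change.** 1. Mark PROMIS at the existing Off Treatment visit for every patient, whatever the reason for stopping.
2. Collect the 6-month form at 6 months from first dose in all patients still in follow-up, whatever their treatment or disease status.
3. Reconcile section 1.2 and footnote h on both the stable-or-better condition and the response-triggered form.
4. In section 13.1, base the 4-week and 6-month change estimates on the time-scheduled forms, and report completion at each time point with the reason for each missing form.

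The cost is one short questionnaire set at a visit that already takes place, a 6-month form for patients who would not otherwise have given one, and wording changes in sections 1.2, 10 and 13.1. Some forms will still be missing after treatment stops, and patients who withdraw from the study altogether cannot be reached at 6 months. Section 13.1 describes stage I enrollment as already past, so the data will mix two schedules and the report should say which patients were under each.

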1.3 Exploratory Objectives

- Compare the rates of epithelioid hemangioendothelioma progression prior to starting trametinib to rates on treatment by central review of radiology images
- Evaluate the effect of trametinib on change in tumor volume and compare to RECIST1.1 response through central imaging review
- Evaluate the effect of trametinib on markers of inflammation including c-reactive protein (CRP), erythrocyte sedimentation rate (ESR) and plasma connective tissue growth factor (CTGF).

2. BACKGROUND

2.1 Epithelioid Hemangioendothelioma

Epithelioid hemangioendothelioma (EHE) is a rare sarcoma that shows vascular (endothelial) differentiation. It usually presents with widespread metastases. Although metastatic disease can be stable for years, it inevitably progresses rapidly and without warning, is highly lethal and has no effective treatment. EHE can occur at any age, but peaks in adulthood (Weiss & Enzinger, 1982). Five-year disease-specific mortality is 40% and 65% for EHE that arises in the lung and liver, respectively (Weiss & Goldblum, 2008). Although localized EHE can often be treated with surgery and radiation, systemic therapy options are limited for patients with metastatic disease in which the median survival is less than 4 years.

Due to the rarity of this disease, there is no consensus on standard systemic therapy and data is limited to single-institution case reports or retrospective case series. Cioffi et al. (Cioffi et al., 2011) reported a retrospective study of 42 patients with metastatic EHE. Thirty-four patients received systemic chemotherapy including conventional doxorubicin-containing regimens (n=16), other chemotherapy regimens (n=6), and anti-angiogenesis agents or tyrosine kinase inhibitors (TKI, n=12). There were no objective responses although 14 patients had stable disease for at least 6 months. Of those with stable disease, 4 patients received doxorubicin-containing chemotherapy, 4 received other chemotherapy and 6 received angiogenesis targeting agents or TKIs. Median PFS was 4.8 months and median OS was 41 months.

Mehrabi et al. published a comprehensive review of patients with malignant hepatic EHE comprised of 434 patients (Mehrabi et al., 2006). The most common treatment was liver transplantation (44.8%), followed by observation (24.8%) and chemotherapy or radiotherapy (21%). One-year and five-year patient survival rates were 73.3% and 30%, respectively, for patients who received treatment with chemotherapy or radiotherapy. Chemotherapeutic regimens were diverse and included thalidomide, doxorubicin, 5-fluorouracil, epirubicin plus dacarbazine and interferon-alpha. Based on the data presented as a retrospective observational analysis, the effectiveness of the different chemotherapy treatments used cannot be inferred.

There have been few clinical trials that have prospectively investigated drug therapies for patients with EHE. For example, a phase II study evaluated bevacizumab in seven patients with locally advanced or metastatic EHE (Agulnik et al., 2013). Two patients had a partial response and four patients demonstrated stable disease with one patient experiencing progressive disease at first evaluation. The mean number of cycles received was 17.3 (52 weeks). Median PFS was 39.1 weeks and median OS was 142.6 weeks. Given the small number of patients in this study, further conclusions cannot be made.

A phase II study by the French Sarcoma Group evaluated the efficacy of sorafenib (800 mg daily) in 15 patients with progressive EHE with a primary endpoint of 9-month PFS (Chevreau et al., 2013). Twelve patients had metastatic disease at the time of enrollment. The 2-month, 4-month, 6-month and 9-month progression free rates were 84.6%, 46.4%, 38.4% and 30.7%, respectively. Median follow-up was 12 months, with a median PFS of 6 months. Median overall survival was not reached at the time of analysis. Two partial responses were noted and lasted 2 months and 9 months. The median treatment duration was 124 days with seven patients requiring dose reductions or transient treatment discontinuation due to toxicity including hand-foot syndrome, diarrhea and mucositis with anorexia. Previously reported treatment and trials have used chemotherapy, immunotherapy, multi-kinase inhibitors or anti-vascular endothelial growth factor inhibitors with marginal benefit; therefore, standard drug therapy for patients with locally advanced or metastatic unresectable EHE has not been established.

Recently, a disease-defining *TAZ-CAMTA1* gene fusion has been identified in EHE. This is a balanced, reciprocal translocation that results in the fusion of *TAZ* (also known as *WWTR1*), to *CAMTA1*, dysregulating the Hippo pathway (Tanas et al., 2016; Tanas et al., 2011). Importantly, this fusion is found in more than 90% of EHE tumors, and EHE tumors have no other consistent genetic alterations, suggesting that the fusion is an early and important genetic event and that EHE cells are highly dependent on *TAZ-CAMTA1* (Tanas et al., 2011). *TAZ-CAMTA1* drives oncogenic transformation through a *TAZ*-like transcriptional program and the Hippo pathway is unable to regulate *TAZ-CAMTA1* (Tanas et al., 2016). Thus, this fusion unleashes an otherwise tightly controlled transcriptional program resulting in EHE oncogenesis. Rubin et al. have studied signal transduction downstream of *TAZ-CAMTA1*, identifying connective tissue growth factor (CTGF) and MAP kinase signaling as key pathways and potential therapeutic targets (unpublished data). Most of the clinical studies discussed above predate the discovery of this gene fusion. The limited success of systemic therapies as demonstrated in these reports underscores the need for further research to identify more effective treatments.

2.2 CTEP IND Agent

2.2.1 Trametinib Dimethyl Sulfoxide (GSK1120212B, MEKINIST)

The RAF-MEK-ERK pathway plays a critical role in multiple cellular functions. Activation of the pathway can result from activation/mutations of the upstream receptor tyrosine kinases (RTKs) and RAS, or upregulation/mutations in RAF and MEK. Upon activation, RAF acts as the MAPK kinase and activates MAPKK (MEK1/2), which in turn catalyzes activation of the effectors ERK1/ERK2. Once activated, ERK1/2 translocate into the nucleus and phosphorylate a number of effector proteins and transcriptional factors that regulate cell proliferation, motility, differentiation, and survival.

Trametinib is one of several MEK inhibitors in clinical development. On May 29, 2013, the U.S. Food and Drug Administration (FDA) approved trametinib for the treatment of patients with unresectable or metastatic melanoma with BRAF^{V600E} or BRAF^{V600K} mutations as detected by an FDA-approved test (U.S. Food and Drug Administration, 2013). On January 10, 2014, the Food and Drug Administration granted accelerated approval to trametinib and dabrafenib for use in combination to treat patients with unresectable or metastatic melanoma with a BRAF V600E or V600K mutation as detected by an FDA-approved test (U.S. Food and Drug Administration, 2014).

Experience to date indicates that MEK is a valid target. In a phase 3 trial comparing trametinib with dacarbazine or paclitaxel in patients with BRAF V600E or V600K mutant metastatic melanoma, trametinib demonstrated a significantly better response rate, progression-free survival, and overall survival (Flaherty *et al.*, 2012). However, single agent activities are limited. Extensive research is underway to identify the patient selection markers and develop rational combination strategies. Preclinical studies have provided strong rationale and proof of principle for combination of MEK inhibitors with RTK inhibitors (EGFR or IGF-1R) (Gopal *et al.*, 2010; Ebi *et al.*, 2011), PI3K/AKT inhibitors (Engelman *et al.*, 2008; Hoeflich *et al.*, 2009), and mTOR inhibitors. On the other hand, the optimal dose/schedule and patient selection criteria for combination regimens have not been defined. Phase 1 results for a number of combinations have been reported, including AZD6244 + MK2206 (Tolcher *et al.*, 2011) and GDC-0973 + GDC-094 (MEK + PI3K inhibitor) (Bendell *et al.*, 2011).

The most up-to-date preclinical and clinical study information for trametinib can be found in the GSK1120212 (trametinib) Investigator's Brochure (August 10, 2018).

